6.0 Laboratory Methods

Specimen processing for peripheral blood mononuclear cells (PBMCs):

Blood will be collected from a vein. Study personnel will collect the blood samples, label without personal identifiers, and deliver to the VUMC Cell Processing Core (Directed by [name]) for preparation of serum and and isolation of peripheral blood mononuclear cells (PBMCs). Serum will be frozen until further testing at Vanderbilt University Medical Center for HAI, MN testing, B and T cell influenza-specific responses. Processing, cryopreservation, storage, and maintenance of sample logs will be done according to standard operating procedures that have been in place and maintained for over 15 years All clinical labs will be sent to the local lab.

Specimen processing for serum:

Whole blood drawn in a tube without anticoagulant will be left at room temperature for a minimum of 30 minutes and maximum of 2 hours. The samples will then be placed at 4°C.

VERSION: 4.0**DATE: November 11, 2019**

Samples will be processed within 24 hours of collection. Tubes will be placed in a table top centrifuge and serum will be clarified by centrifugation at 3000 rpm for 10 minutes at 4°C. Serum will be aliquotted into labeled cryovials with an adjustable pipette. Aliquot size will be determined based on the testing to be performed. Serum will then be stored at -80°C in labeled fiberboard boxes until shipping or testing is performed.

HAI Assay:

The hemagglutination inhibition assay (HAI) assay is adapted from the CDC laboratory-based influenza surveillance manual and we have extensive experience in its use. Briefly, three parts of receptor destroying enzyme (RDE) will be added to one part sera and incubated overnight in a 37°C water bath. Then the RDE will be inactivated by incubation in a 56°C water bath for 30 minutes. Following inactivation of RDE, PBS will be added to the sample for a final serum concentration of 1:10. Turkey red blood cells (RBC) will be washed twice and diluted in PBS to a final concentration of 5% RBC. The cells are kept at 4°C and expire in one week. Twenty-five microliters of RDE-treated sera are then serially diluted across the plate (2-fold). Twenty-five microliters of prepared flu antigen tittered to 4HAU is added to the diluted sera. The plates are then incubated at room temperature for 30 minutes followed by the addition of 50 µl of 5% turkey RBC. Then, the plates are mixed and the RBCs are allowed to settle for 1 hour at room temperature. The test will be read by observing a lack of agglutination in the button RBC that is settled in the bottom of the well. The HAI titer is determined by the reciprocal dilution of the last well with lack of agglutination. Every plate will have a virus and a serum control. The virus control will consist of PBS + 4HAU of antigen + turkey RBC. The cell control will consist of PBS + RBC. A negative titer is reported as a <10. All samples are tested in duplicate and results are expected to be +/- one well. If duplicate results are more than one well different the sample will be repeated. The lower of the two results within one well will be recorded as the titer.

7.0 Statistical Analysis:

This is an exploratory study. Antibody titers will be compared pre- and post-vaccination on the samples collected. Paired measures of cell mediated immunity will be compared before and after vaccination. In addition, post-vaccination measures of cell mediated immunity will be compared across age strata and correlated with serologic response to vaccination. Analyses will be done accounting for age, frailty, and underlying medical conditions.

Data Management: All data will be collected and stored under the REDCap database system. This system is a secure web application for building and managing online surveys and databases. While REDCap can be used to collect virtually any type of data, it is specifically geared to support data capture for research studies. The REDCap Consortium is composed of 1,920 active institutional partners in 103 countries who utilize and support REDCap in various ways including the CDC. The REDCap application allows users to build and manage online surveys and databases quickly and securely, and is currently in production use or development build-status for more than 273,000 projects with over 372,000 users spanning numerous research focus areas across the consortium. This system will allow each site to access the database and will provide a secure means to send a study dataset without personal identifiers upon request to the CDC.

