4. **The Montreal Cognitive Assessment (MoCA):** The MoCA is a validated, performance-based tool used to detect cognitive impairment with score ranges from 0 to 30 points. It will be administered at enrollment. The following ranges may be used to grade severity: 18-26 = mild cognitive impairment, 10-17 = moderate cognitive impairment and < 10 = severe cognitive impairment. This tool will be included as many geriatricians feel cognitive impairment is often associated with frailty. As presence of depressive symptoms may affect cognition and memory, we will also include a depression symptom screen as part of the assessment. All participants will complete the Patient Health Questionnaire as part of routine care. The results of the Patient Health Questionnaire performed during routine medical care will be included in the chart review.
5. **Baseline clinical laboratory assessment**

At the first visit, blood specimen collection will also include evalution of two clinical tests to be conducted by the Vanderbilt Laboratory: CMV serology and CD4/CD8 lymphocyte ratio calculation. Detection of serum CMV IgM and IgG antibodies will be conducted on all participants. Calculation of absolute CD4 and absolute CD8 lymphocytes will also be performed using the clinical lab for calculation of CD4/CD8 ratio. Inversion of the CD4/CD8 in older adults has been found to correlate with measures of adaptive immune senescence, CMV seropositive, as well as frailty and falls ⁶³⁻⁶⁵.

	Visit 1 (D0)	Visit 2 (D7[+/2days])	Visit 3 (D28 [-4/±14 days])	Visit 4 (Month 6/ D180[+/-14 days]) Optional
Baseline Data Collection: - Case report form - Frailty Metrics - 5STS - MoCA	X			

- Clinical laboratory tests				
Blood Draw	X	X	X	X
Vaccination	X			

Recruitment and Retention: Although most industry-sponsored vaccine studies in older adults seek to recruit a very healthy, mobile population, in this study we will pay special attention to the enrollment of older adults ≥ 80 years of age and those who are frail so we can get a more comprehensive assessment of the safety and immunogenicity of these two vaccines in a larger spectrum of older adults. The population in Davidson County is 61% white and 27% black with 37,787 women and 25,574 men ≥ 65 years of age who reside in the County.

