Informed Consent in Older adults: Previous research conducted by our group to identify viral respiratory disease in hospitalized patients has led our team to work closely with our Institutional Review Board to improve the consenting process for older adults. Consents have been simplified to include only necessary information and they are printed in larger fonts. Each enroller also utilizes magnifiers and hearing amplifiers to assist the participants. In addition, we also have utilized a standardized assessment to determine a person's ability to self-consent wherein they are asked specific questions to determine their understanding of the consent form. These practices will be used for the proposed study.

Table : Enrollment Plan for 2019-2020

Samples (100 subjects)	Tests	Amount of Blood/Participant
Prevaccination (Day 0)	PBMC/HLA + Ab + CBC w/diff	45 ml +10 ml + 10ml = 65 ml
Day 7 (+/- 2 days)	PBMC + Ab + CBC w/diff	45 ml +10 ml + 10 ml= 65 ml
Day 28 (-4/+14 days)	PBMC + Ab + CBC w/diff	45 ml +10 ml + 10 ml= 65 ml
Month 6/Day 180 (+/- 14 days)	PBMC + Ab + CBC w/diff	45 ml +10 ml + 10 ml= 65 ml
Total		270 ml

PBMC = peripheral blood mononuclear cells

Ab= antibody

Approximately 100 adults ≥ 65 years of age will be enrolled. After consent, blood and serum will be collected and then subjects will be randomized to either high dose influenza vaccine or adjuvanted influenza vaccine (both FDA approved vaccines). Vaccination will be done by an unblinded nurse. All further evaluations and analysis will be done by a blinded staff member. Medical history, relevant medications, and frailty status will be assessed at the first visit. Subjects will return (Table 3) for blood and serum draws on days 7 (+/- 2 days), 28 (-4/+14 days) and for an optional visit at 6 months/180 days (+/- 14 days) (after influenza season).

Influenza vaccination

The ACIP recommends influenza vaccine for all adults ≥ 65 years of age. This includes the egg-based vaccines, the cell-based vaccines and the recombinant vaccines. This study will use the egg-based high-dose inactivated influenza (IIV-HD), the egg-based adjuvanted influenza vaccine (aIIV), and the recombinant influenza vaccine (rIIV). Each of these vaccines are recommended and licensed in adults ≥ 65 years of age and will be used in this study according to licensure.

[figure not shown]
VERSION: 4.0

DATE: November 11, 2019

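### Participants are randomised between vaccines, but Section 7.0 plans no analysis by arm and adjusts for neither arm nor Day 0 titre, so the randomised comparison goes unused

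*Combined protocol and SAP*

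**What the plan says.** Section 7.0 (Statistical Analysis) opens with "This is an exploratory study" and then plans four things:

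- On serology: "Antibody titers will be compared pre- and post-vaccination on the samples collected".
- Cell-mediated immunity is compared within person, before against after vaccination.
- Finally, in one sentence covering two analyses, "post-vaccination measures of cell mediated immunity will be compared across age strata and correlated with serologic response to vaccination".

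The adjustment sentence is "Analyses will be done accounting for age, frailty, and underlying medical conditions". Vaccine arm is not mentioned anywhere in the section. Day 0 titre appears only as the earlier half of the pre/post comparison. The term for serologic response is not defined, so it may or may not incorporate baseline.

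The design sections point towards a comparison of vaccines. Subjects Randomized specifies 1:1:1 allocation. The Enrollment Plan has an unblinded nurse vaccinate, with later evaluation and analysis blinded, and collects antibody serum at Day 0. Recruitment and Retention speaks of "a more comprehensive assessment of the safety and immunogenicity of these two vaccines".

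The number of arms is not settled. Recruitment and Retention refers to two vaccines, and the Enrollment Plan says "subjects will be randomized to either high dose influenza vaccine or adjuvanted influenza vaccine". Aim 2, the Influenza vaccination text and the 1:1:1 ratio all imply three. The target is 120 each year under Accrual Goal and about 100 in the Enrollment Plan.

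**The concern.** A pre/post comparison pooled over arms estimates the average rise across whichever vaccines were given. It carries no information on the difference between them. The trial goes to the trouble of random allocation and blinded analysis, yet has no analysis that uses either for a vaccine contrast.

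If arms are compared later without a stated model, several choices would be made after the data are seen: Day 28 titre, change score or baseline-adjusted titre, and what value to give results below the assay limit. On the last, the HAI Assay text says only "A negative titer is reported as a <10".

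The same covariate list governs the models of vaccine response in Aim 2 and in the response parts of Aims 3 and 4. Any difference between vaccines there is left in the residual. Day 0 titre is also left out, although the Background itself says that earlier exposure to influenza and its vaccines moderates response.

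**Working it through.** The documents give no SD, correlation, effect size, alpha, power or dropout, so there is no stated figure to reproduce. Only the allocation (1:1:1) and the two targets (120 and about 100) come from the text. Everything else below is assumed.

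**1. Precision of a between-arm contrast**

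Inputs: three arms; n = 40 per arm (120/3) or 33 (about 100/3); residual SD 2 log2 given the planned covariates; pre/post partial correlation ρ = 0.3/0.5/0.7; no dropout.

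The 95% CI of a pairwise GMT ratio is the estimate divided and multiplied by 2^(t × SD × √(f × 2/n)), where:

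- f = 1 for unadjusted Day 28 titre;
- f = 2(1 − ρ) for a change score (equal SD before and after);
- f = 1 − ρ² with Day 0 titre as a covariate.

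Degrees of freedom are 3n − 3 arms − 3 covariates, less one more with Day 0 titre. At n = 33, unadjusted: df = 93, t = 1.986, 2√(2/33) = 0.492, and 2^(1.986 × 0.492) = 1.97.

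| n per arm | Unadjusted | Change score, ρ 0.3/0.5/0.7 | Day 0 adjusted, ρ 0.3/0.5/0.7 |
|---|---|---|---|
| 40 | 1.85 | 2.07/1.85/1.61 | 1.80/1.70/1.55 |
| 33 | 1.97 | 2.23/1.97/1.69 | 1.91/1.80/1.62 |

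Other assumptions, unadjusted against Day 0 adjusted:

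- SD 1.5 at n = 33, ρ = 0.5: 1.66 to 1.55. SD 2.5: 2.33 to 2.08.
- 10% of Day 28 samples missing, ρ = 0.5: 1.91 to 1.75 at 36 per arm and 2.04 to 1.85 at 30 per arm.
- Two seasons pooled (80 per arm), ρ = 0.5: 1.54 to 1.45.

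**2. Does the assay floor remove the gain?**

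Simulation: three arms of 40, 4,000 runs, SD 2, mean rise 1.5 log2, one arm higher by 1 log2, titres read in 2-fold wells from 10, and <10 set to 5. The adjusted/unadjusted variance ratio was 0.92/0.79/0.57 when 23% of Day 0 titres were below 10, and 0.94/0.78/0.59 when 40% were. Without a floor, 1 − ρ² is 0.91/0.75/0.51. Most of the gain survives. The true 1 log2 difference was estimated at 0.97-0.99 and 0.92-0.93 log2 respectively, so the rule for <10 should be stated and checked.

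**3. Leaving arm out of the vaccine-response models**

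For three equal, equally spaced arms with extreme range R, the added residual variance is (R²/6)/SD². The standard error (SE) grows by √(1 + that) − 1.

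| R (log2) | Added variance, SD 2.5 to 1.5 | Added SE |
|---|---|---|
| 0.5 | 0.7-1.9% | 0.3-0.9% |
| 1 | 2.7-7.4% | 1.3-3.6% |
| 2 (4-fold) | 10.7-29.6% | 5-14% |

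Arm is randomised, so in expectation it is independent of age, frailty, CMV status and Day 0 senescence profile. Its omission adds noise but no expected bias.

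**4. Which parts of the aims this reaches**

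Aims 3 and 4 each have two parts. One links CMV or frailty to senescence; the other links it to vaccine response. If senescence is measured at Day 0, an arm assigned afterwards cannot explain it. The loss is therefore confined to Aim 2 and the response parts of Aims 3 and 4.

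**5. Strains**

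Aim 2 calls the adjuvanted vaccine aIIV3. The Background gives the recombinant vaccine as 45 mcg per strain and 180 mcg in total, and 180/45 = 4 strains. A per-strain comparison may meet a strain that one vaccine lacks.

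**The case against.** The strongest reply is that the study is exploratory, no numbered aim states a vaccine contrast, and the phrase about assessing the vaccines sits in recruitment text. All of that stands. A reader might infer that the trial lacks its primary analysis; the documents name no such analysis, so that reading fails. What remains is that random allocation and blinded analysis have no matching analysis, and exploratory status does not remove the value of stating a model before the data are seen.

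A reader might also infer that Aims 2-4 as a whole lose precision, or that omitting arm biases them. Neither is supported: the senescence parts cannot gain from arm, the response parts lose little unless the vaccines differ greatly, and randomisation removes expected bias.

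It can also be said that unadjusted Day 28 titre is not the natural comparator, since the planned serology is pre/post. This is fair. Against a change score the gain from adjustment is larger at low correlation (2.23 to 1.91) and small at high correlation (1.69 to 1.62). The direction is the same in either case.

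Finally, the conflicts over arms and target are separate consistency defects. They add no weight here, but must be settled before an arm term can be written.

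**Conclusion.** The point holds as an unused comparison. Section 7.0 has no by-arm analysis and its covariates omit arm and Day 0 titre; both facts can be read directly from the text.

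The size of the benefit rests on assumed values. At about 100 participants in three arms, Day 0 adjustment narrows the interval for a vaccine contrast noticeably at correlations of 0.5 or more if the alternative is unadjusted titre, and at correlations of 0.5 or less if it is a change score. The cost of omitting arm from the response models is minor for differences up to 2-fold. No passage gives the size of any difference between vaccines.

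Day 0 titre needs separate treatment in the response models. It is not randomised with respect to senescence, CMV status or frailty, so including it can change the association as well as its precision. The documents do not say which association is wanted, so they do not support calling either model the correct one. Worth fixing, because the change is cheap and uses data already collected.

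**What to change.** 1. Reconcile the number of arms (Aim 2, Recruitment and Retention, Enrollment Plan, Influenza vaccination, Subjects Randomized) and the enrolment target (Accrual Goal, Enrollment Plan).
2. Add to Section 7.0 an exploratory linear model of Day 28 log2 HAI (and MN) titre on randomised arm, Day 0 log2 titre and the three covariates already planned, plus season if seasons are pooled. Fit it per strain, and compare arms only on strains that all compared vaccines contain.
3. State a rule for titres <10, for example set to 5, with an interval-censored model as a check.
4. Report between-arm GMT ratios with 95% CIs, labelled exploratory and without multiplicity adjustment. Keep pre/post change as descriptive.
5. Include arm (and season if pooled) in the vaccine-response models of Aims 2-4 only, and report those models with and without Day 0 titre.

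Cost: wording in Section 7.0, two degrees of freedom for three arms, one for Day 0 titre, and any season terms. No new samples or visits.

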4.0 Inclusion/Exclusion Criteria

Inclusion Criteria

1. Age ≥ 65 years
2. Independent Living (including Assisted Living)

Exclusion Criteria

1. Unable to understand the consent or the study.
2. Allergic to any vaccine components, excluding eggs.
3. History of Guillain-Barre.
4. Anaphylaxis egg allergy
5. Residing in a long-term care facility such as a nursing home.

5.0 Study procedures:

Data Collection: During the first year of the study, the following forms will be designed to complete the objectives of this study.

1. **REDCap Case Report Form:** Administered by the enrollers, and includes: demographics; height and weight; past medical history; history of recent falls and hospitalizations; active medications; alcohol use; use of home oxygen; questions regarding ability to perform activities of daily activity; frailty measures (see section on Frailty Metrics); sarcopenia assessment; depression symptom screen; cognitive assessment; and contact information for the participant.
2. **Frailty Metrics:** As mentioned earlier, the evaluation of frailty is very important in the assessment of vaccine responses. Frailty can be measured by multiple methods. One of the most accepted tools is the Fried Frailty Evaluation.⁴⁹ This tool evaluates shrinkage (loss of mean body mass), weakness, endurance, slowness, and physical activity on a scale of 0-5. This tool is predictive of falls, worsening mobility or disability in the activities of daily living, and in predicting hospitalization and death over a three-year period. This measure of frailty is not synonymous with comorbidities or functional status. A composite frailty measure will be calculated using each of the evaluation scales and utilized to compare the safety profile and ultimately the immune responses.⁶¹ This measure will be based on the five parameters of weight loss, exhaustion, low activity level, slowness, and weak strength, described below.

1. Weight Loss	
Meets criteria for frailty if answers yes to: Self-report of loss of >10 pounds unintentionally over the past year
						

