2. Exhaustion	
Meets criteria for frailty if answers: Self-report of “moderate” or “most of the time” for either:
 
 1. I felt that everything I did was an effort in the last week: 
 a. Rarely or none of the time (<1 day) b. Some or little of the time (1-2 days) c. Moderate amount of the time (3-4 days) d. Most of the time 2. I could not get going in the last week: 
 a. Rarely or none of the time (<1 day) b. Some or little of the time (1-2 days) c. Moderate amount of the time (3-4 days) d. Most of the time 						
3. Low Activity Level	
Meets criteria for frailty if answers: Self-reported “limited a lot” for: Does your health limit vigorous activities such as running, lifting heavy objects, or participating in strenuous sports?
 
 a. No, not at all b. Yes, limited a little c. Yes, limited a lot 						
4. Slowness	
Meets criteria for frailty if: Time to walk 15 feet (4.57 meters) at usual pace (averaged over 2 trials)
 
 
 Men	Women	
 
 $\geq 7\text{sec}$ for height $\leq 173\text{cm}$	$\geq 7\text{sec}$ for height $\leq 159\text{cm}$	
 
 $\geq 6\text{sec}$ for height $> 173\text{cm}$	$\geq 6\text{sec}$ for height $> 159\text{cm}$	
 
	Men	Women	$\geq 7\text{sec}$ for height $\leq 173\text{cm}$	$\geq 7\text{sec}$ for height $\leq 159\text{cm}$	$\geq 6\text{sec}$ for height $> 173\text{cm}$	$\geq 6\text{sec}$ for height $> 159\text{cm}$
Men	Women						
$\geq 7\text{sec}$ for height $\leq 173\text{cm}$	$\geq 7\text{sec}$ for height $\leq 159\text{cm}$						
$\geq 6\text{sec}$ for height $> 173\text{cm}$	$\geq 6\text{sec}$ for height $> 159\text{cm}$						

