5. Weakness	
Meets criteria for frailty if: Grip strength measured by hand dynamometer (averaged over 3 trials of dominant hand):
 
 
 Men	Women	
 
 ≤ 29kg for BMI ≤ 24	≤ 17kg for BMI ≤ 23	
 
 ≤ 30kg for BMI 24.1-26	≤ 17.3kg for BMI 23.1-26	
 
 ≤ 30kg for BMI 26.1-28	≤ 18kg for BMI 26.1-29	
 
 ≤ 32kg for BMI >28	≤ 21kg for BMI >29	
 
 
(BMI: body mass index)
	Men	Women	≤ 29kg for BMI ≤ 24	≤ 17kg for BMI ≤ 23	≤ 30kg for BMI 24.1-26	≤ 17.3kg for BMI 23.1-26	≤ 30kg for BMI 26.1-28	≤ 18kg for BMI 26.1-29	≤ 32kg for BMI >28	≤ 21kg for BMI >29
Men	Women										
≤ 29kg for BMI ≤ 24	≤ 17kg for BMI ≤ 23										
≤ 30kg for BMI 24.1-26	≤ 17.3kg for BMI 23.1-26										
≤ 30kg for BMI 26.1-28	≤ 18kg for BMI 26.1-29										
≤ 32kg for BMI >28	≤ 21kg for BMI >29										

Participants with total scores of 3 or greater meet criteria for frailty. Those participants with a higher composite score (and therefore a greater degree of frailty) will be expected to have lower reactogenicity to vaccine and likely a lower serologic response, but this hypothesis will be tested.

3. **Five-times Sit-to-Stand (5STS) Test for Sarcopenia.** All participants will be undergo two trials of timed duration to go from sitting position to standing position and back to sitting five times. The average of the 2 trials will be used for the result. The 5STS is a routinely-used geriatric assessment for sarcopenia and fall risk. An average 5STS time of >12 seconds is indicative of fall risk ⁶².

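### Sex is not among the named adjustment factors, so the between-person analyses for Aims 2 to 4 and across age strata may be confounded by it; adding it costs almost nothing

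*Combined protocol and SAP*

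**What the plan says.** The statistical plan is one short paragraph, Section 7.0. It opens with "This is an exploratory study" and describes paired comparisons before and after vaccination, comparison of post-vaccination cell-mediated immunity across age strata, and correlation of that immunity with serologic response. It closes with "Analyses will be done accounting for age, frailty, and underlying medical conditions". No model is written out. Sex is not named as a covariate or stratification factor anywhere; gender appears only as an example in the generic REDCap help text reproduced under randomisation.

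Sex must nevertheless be available. Under Frailty Metrics in Section 5.0, two of the five items have separate columns for men and women:
- Slowness: "Time to walk 15 feet (4.57 meters) at usual pace (averaged over 2 trials", with the height split at 173 cm for men and 159 cm for women.
- Weakness: "Grip strength measured by hand dynamometer (averaged over 3 trials of dominant hand", with cut-offs by sex and BMI band, for example 29 kg for men and 17 kg for women in the lowest band.

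The case report form "includes: demographics; height and weight; past medical history". Sex is not listed by name, but it would normally fall under demographics.

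**The concern.** Aims 2, 3 and 4 relate an immune senescence profile, CMV-specific responses and frailty to vaccine response or to one another. All of these are characteristics that people bring to the study. The 1:1:1 allocation protects comparisons between vaccines, but not comparisons of frail with non-frail, or of people with more and less senescent profiles. The same holds for the age-strata comparison. Covariate adjustment is the only protection that the plan describes for these analyses, and sex is not in it.

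If sex is related both to the exposure (frailty, senescence or age group) and to the immune outcome, part of a sex difference would be reported as an effect of that exposure. Leaving the matter open also allows the choice to be made after the data are seen.

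**Working it through.** **Plan's own figure.** There is none to reproduce: the plan gives no effect size, SD, alpha or power. What follows is an illustration for the frail versus non-frail contrast in log2 titre.

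**Inputs from the documents**
- Sample size: about 100 (enrolment plan for 2019-2020). The accrual goal gives 120 per year.
- Source population (Recruitment and Retention): "37,787 women and 25,574 men ≥ 65 years of age who reside in the County". Share of women p = 37,787 / (37,787 + 25,574) = 37,787 / 63,361 = 0.596, so p(1 − p) = 0.241. This is a county figure used as a stand-in for the sample.

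**Assumed inputs (not in the documents)**
- d, the sex difference in log2 titre: 0.2 to 0.8.
- D, the share of women among the frail minus that among the non-frail: 0.1 to 0.3.
- Outcome SD: 1.5 log2.
- Share frail, f: 15% or 30%.

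**Step 1: bias if sex is left out.** Bias = d × D.
- Low: 0.2 × 0.1 = 0.02 log2.
- Middle: 0.5 × 0.2 = 0.10 log2.
- High: 0.8 × 0.3 = 0.24 log2.
- If either d or D is zero, the bias is zero.

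**Step 2: standard error of the contrast.** SE = SD / √(n f (1 − f)).
- f = 0.30: 1.5 / √(100 × 0.21) = 0.33 log2.
- f = 0.15: 1.5 / √(100 × 0.1275) = 0.42 log2.

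**Step 3: bias relative to noise**

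| Bias (log2) | In SE, 15% frail | In SE, 30% frail |
|---|---|---|
| 0.02 | 0.05 | 0.06 |
| 0.10 | 0.24 | 0.31 |
| 0.24 | 0.57 | 0.73 |

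At 0.73 SE, a nominal two-sided 5% test of a true null would reject with probability Φ(−1.96 + 0.73) + Φ(−1.96 − 0.73), about 11%. At 0.31 SE the figure is about 6%.

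**Step 4: what adding sex does to the standard error.** Let r = D √(f(1 − f)) / √(p(1 − p)) be the correlation of sex with frailty, and R² = (d/SD)² p(1 − p)(1 − r²) the outcome variance that sex explains beyond frailty. The SE ratio, adjusted to unadjusted, is √[ (1 − R²)/(1 − r²) × (n − 2)/(n − 3) ].

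| d | D | Ratio, 15% frail | Ratio, 30% frail |
|---|---|---|---|
| 0.8 | 0.1 | 0.973 | 0.975 |
| 0.5 | 0.2 | 1.003 | 1.010 |
| 0.8 | 0.3 | 0.996 | 1.013 |
| 0.2 | 0.3 | 1.028 | 1.045 |

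Over the assumed grid the change runs from about a 3% gain to about a 5% loss. Adding sex is close to neutral for precision, so the case for it rests on bias and prespecification.

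**The case against.** Four arguments on the other side have weight.

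1. **Confounding is possible, not shown.** A reader might infer that the frailty and senescence effects are confounded by sex, and that the sex-specific cut-offs prove it. The documents do not support this. Nothing in them links sex to frailty prevalence, senescence, T-cell measures or titre. Cut-offs set by sex score each person against a same-sex standard, which tends to weaken a link between sex and frailty in those items. This stands. It does not remove the possibility: three of the five items have one rule for both sexes, the walk times are the same 7 s and 6 s for men and women, and recruitment pays special attention to the frail and to people aged 80 or over. Sex balance between the groups is therefore not assured.

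2. **Precision.** A reader might also infer that leaving sex out makes the estimates less precise than they could be. Step 4 shows that this is not assured; in several cases adjustment slightly widens the interval.

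3. **Scope.** Comparisons of the same person before and after vaccination are largely unaffected, because a constant sex difference cancels. The illustration covers frailty only. For senescence and age the structural argument is the same, but no size has been worked out.

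4. **The sentence may not be a closed list.** It also omits CMV status and vaccine arm, and the study is exploratory. That is fair. But if the list is open, naming sex costs nothing; if it is closed, sex is unhandled. Exploratory status does not remove bias from an association estimate.

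Separate results for men and women are not needed to settle this. If enrolment mirrored the county, 100 participants would include about 40 men (25,574 / 63,361 = 0.404), of whom 6 to 12 would be frail at 15% to 30%. Such results could only be descriptive.

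**Conclusion.** The point holds as a minor one. Sex is missing from the named adjustment factors, it must be on hand to score frailty, and the analyses for Aims 2 to 4 and across age strata are not protected by randomisation. They may be confounded by sex; the documents do not allow anything firmer. In the frail versus non-frail contrast the possible bias runs from negligible (0.02 log2, about 0.05 SE) to 0.24 log2 (about 0.7 SE with n = 100 and 30% frail). The upper figure needs the extreme of both assumed ranges at once. The sex difference, the imbalance in share of women, the SD and the frail share are all assumptions, and the share of women is a county figure. No gain in precision should be claimed.

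**What to change.** In the last sentence of the Section 7.0 analysis paragraph, add sex after age in the list of factors, and state that it applies to the between-person analyses: Aims 2 to 4 and the comparisons across age strata. If the investigators prefer to leave it out, give the reason. It would also help to name sex explicitly among the demographics on the case report form.

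Cost: one word and one degree of freedom, no new data collection, and a change in standard error of between about a 3% gain and a 5% loss under the ranges above.
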